5.8 Safety ECG (12-lead ECG) and Holter Monitoring

6 OTHER ANALYSES

6.1 Interim Analyses

Sponsor may plan an unblinded interim analysis at time when sufficient number of patients have finished 12 weeks of treatment. If sponsor decides to perform an interim analysis, it will be operated by an independent Data Monitoring Committee (DMC).

6.2 Subgroup Analyses

Subgroup analyses for the primary efficacy endpoint (i.e., improvement of 3-component Mayo Clinic Score consisting of subscores for stool frequency, rectal bleeding and findings of endoscopy at Week 12) and other important efficacy endpoints will be performed in order to explore whether the treatment effects are consistent across different subgroups. The baseline patient characteristics below are the subgroup factors to be explored.

- Sex (Male, Female)
- Age: $>$ or \leq median age, \geq or $<$ 65 years
- Race
- Presence or absence of current oral corticosteroid usage
- Previous exposure to TNF α antagonists
- Responders vs. subjects who had inadequate / loss of response in previous exposure to TNF α antagonists

[REDACTED]

- Baseline Total Mayo score ≤ 8 vs > 8 .

The change from baseline in 3-component Mayo Clinic Score at Week 12 using an ANCOVA model with terms for treatment, subgroup, treatment-by-subgroup interaction, and baseline value as covariate will be provided. Least-squares mean (LSM) by treatment group for each of the subgroups and its 90% confidence interval (CI), and least-squares mean difference between treatment group for each of the subgroups and its 90% CI will be reported. A forest plot for all subgroups will be presented for the least-squares mean differences.

In addition to the subgroup analyses for the primary endpoint, the following analyses will be performed:

[REDACTED]

6.3 Multiplicity

Primary comparison is between APD334 2 mg vs placebo [REDACTED]

The primary analysis will compare PMS#1 change from baseline between treatment groups using a one-sided test at the 0.05 level of significance and 90% CI will be reported. If the result is significant, the primary hypothesis will be considered satisfied and this study will be declared positive. If this primary test is significant the secondary testing will proceed as following.

[figure not shown]
Secondary endpoints:

1. Proportion of patients who achieve endoscopic improvement at Week 12
2. Improvement in 2 component Mayo score (score ranging from 0 to 6, including rectal bleeding and findings on endoscopy) at Week 12
3. Improvement in Total Mayo Clinic Score (score ranging from 0 to 12, including stool frequency, rectal bleeding and findings on endoscopy, and physician's global assessment) at Week 12.

If the primary testing is significant, testing for secondary endpoints will proceed in pre-specified order. Provided that all previously specified tests are statistically significant ($p < 0.05$), each of these comparisons will be assessed using the one-sided test at the 0.05 level of significance. However, if a comparison is not statistically significant, then subsequent comparison(s) will be considered exploratory.

Exploratory endpoints:

- The trichotomous composite endpoint of clinical remission and clinical response (score ranging 0 to 2: score 2 for achieving both clinical remission and clinical response; 1 for achieving only clinical response, and 0 for achieving neither) at Week 12.
- The proportion of patients achieving clinical remission at Week 12
- Proportion of patients who achieve clinical response at Week 12

Non-formal statistical testing on treatment effect will be performed and reported along with nominal p-values.

6.4 Statistical Assumptions Checking

For score or continuous measures, the assumptions for ANCOVA may be checked by the following tests:

- parallel regressions tested in a supplemental ANCOVA that includes baseline by treatment interaction term
- assumption of homogeneous variability between groups may be tested, using Levene's test or the Brown-Forsythe test, whichever appropriate
- visual inspection of linearity of regression

If there is evidence of gross violation of the assumptions for ANCOVA, then the offending endpoint may be analysed by ordinal logistic regression.

For categorical measures, if a logistic model gives non-estimable odds across a treatment group due to complete or quasi-separation then the variable causing the separation may be removed from the model. This may be noted in the results table.

If the proportional odds assumption in an ordinal logistic regression model is violated, which is indicated by $p\text{-value} < 0.05$ by score test for the proportional odds assumption, then treatment effects may be estimated using analysis of covariance (ANCOVA).

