9.2 Sample Size and Power Calculations

For the comparison of the proportion of patients who achieve clinical remission between APD334 versus placebo, a sample of ~80 patients per group will provide 80% power to detect a difference of 18% (from 10% to 28%) at $\alpha=5\%$ (2-sided test). This calculation is based upon an assumed placebo rate of 10%.

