7.2 Method of Assigning Participants to Treatment Groups Study

Patients who meet all the entry criteria and are eligible for the study will report to the investigator to be randomized on Day 1. Sites will randomize eligible patients for entry into the study in a 1:1:1 ratio to receive once daily doses of 1 mg APD334, 2 mg APD334, or matching placebo across the entire study, and is not constrained within a center. Randomization will be stratified by presence or absence of current oral corticosteroid usage and previous exposure to TNF α antagonists. All pre-specified efficacy analysis model will include for these two factors using CRF recorded data. Potential discrepancy between CRF recorded data and IVRS data entered by site staff will be investigated. A post-hoc analysis may be performed to evaluate the impact on main study endpoints caused by such discrepancy.

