Whether the missing data pattern is monotone or arbitrary (non-monotone), a fully conditional specification (FCS) method^{11,12} with predictive mean matching for continuous variables^{13,14} can be used. The FCS method allows for separate conditional distributions for each imputed variable. The predictive mean matching approach creates a regression model using parameters sampled from the posterior distribution and then a predicted value for each missing value is computed. The missing value is replaced by randomly selecting an observation from a set of ‘k’ values that are the closest predicted values to the missing predicted value.

In the case of Mayo scores, a multiple imputation approach is implemented for the missing individual components of the Total Mayo Score (TMS), which include stool frequency, rectal bleeding, findings of flexible proctosigmoidoscopy (endoscopy), and physician global assessment. Each individual subscore is imputed and then the composite endpoint measures are created (see list of endpoints below) following the specified algorithms or formulas in the SAP. The rectal bleeding, stool frequency, endoscopy, physician’s global assessment, treatment, stratification factors (oral corticosteroid use and prior exposure to TNF α antagonists), biomarker variables (e.g. [REDACTED]) inform the imputation model. The imputation model may include all these variables at all planned time points (e.g. Screening, Baseline, Week 1, 2, 4, 8, 12 and may be specific for each variable). These variables are included because they are correlated with the endpoint and/or missingness. The multiple imputation process creates [REDACTED] complete datasets using PROC MI in SAS 9.4. During post-processing, the endpoints are derived in each of the [REDACTED] complete datasets. The endpoints and analysis model in parentheses are listed below:

- PMS#1 (bleeding, stool, endoscopy) change at Week12 (ANCOVA)

[figure not shown]
- %-endoscopic improvement at W12 (Logistic regression)
- 2-component Mayo scores (bleeding, endoscopy) change at Week12 (ANCOVA)
- Total Mayo score (4-component) change at Week12 (ANCOVA)
- [REDACTED]
- %-clinical remission at Week12 (Logistic regression)
- %-clinical response at Week12 (Logistic regression)
- [REDACTED]
- Endoscopic score change at Week12 (ANCOVA)
- [REDACTED]
- Combination of clinical remission and response (trichotomy) at Week12 (Ordinal Logistic)

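### SAP 6.4 lets treatment or a stratification factor be dropped from a logistic model when separation occurs, and reporting the removal is optional

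*SAP*

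**What the plan says.** SAP 6.4 covers assumption checks for all efficacy models. For categorical measures the trigger is a logistic model whose odds cannot be estimated across a treatment group; the text continues: "due to complete or quasi-separation then the variable causing the separation may be removed from the model". The only reporting provision is "This may be noted in the results table". The section names no alternative estimator and protects no term.

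Other sections bear on this:

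- SAP 7.2, on the two stratification factors (oral corticosteroid use and prior TNFα antagonist exposure): "All pre-specified efficacy analysis model will include for these two factors using CRF recorded data".
- SAP 7.4.1 lists the models to be run on the imputed data, including "endoscopic improvement at W12 (Logistic regression") and "clinical remission at Week12 (Logistic regression"), and likewise logistic regression for clinical response. Estimates and standard errors are pooled by Rubin's formula.
- SAP 4.3 puts all three arms in one treatment term for the individual comparisons.
- SAP 4.3.2 specifies a stratified CMH test and risk difference with a 90% CI for endoscopic improvement. SAP 4.3.3 applies similar analyses to remission and response, and adds logistic regression for dose response on categorical variables.
- Protocol 9.2 gives the only binary event rates in the documents, 10% and 28% remission, and says: "This calculation is based upon an assumed placebo rate of 10" (per cent).

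**The concern.** The trigger in SAP 6.4 is worded in terms of a treatment group. When one arm has no events, or only events, the variable that separates the outcome is treatment. Following the rule to the letter takes treatment out of the model, and no logistic treatment effect remains. Because treatment is a single three-level term, one empty arm also costs the contrast between the other two arms. With an empty placebo arm, for example, 2 mg versus 1 mg could still be estimated but would be lost.

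If a stratification factor separates instead, removing it keeps the treatment contrast but departs from SAP 7.2, which states no exception.

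Multiple imputation adds a third difficulty. Separation can occur in some imputed datasets and not in others. SAP 6.4 does not say whether a term is then dropped everywhere or only where the fit fails. In the second case Rubin's formula would average coefficients from different models.

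The choice would be made on unblinded results, with no criterion and no duty to report it. Endoscopic improvement, the first secondary endpoint in the fixed sequence of SAP 6.3, is among the endpoints listed for logistic regression.

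**Working it through.** **Inputs.** 39 evaluable patients per arm, difference 1.15, SD 2.03, one-sided α = 0.05 (SAP 7.1). Remission 10% on placebo and 28% on active (Protocol 9.2). About 10% missing Week 12 endoscopy (SAP 9). The 5% and other placebo rates below are assumptions that show the range.

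**1. The plan's own figure.** n per group = 2(1.645 + 0.842)² × 2.03² / 1.15² = 38.5, rounded up to 39. This reproduces SAP 7.1; power at 39 is 80.4% by the normal formula and 79.8% by the noncentral t. The separation rule itself carries no figure.

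**2. Chance of an empty arm.** P(no events) = (1 − p)ⁿ.

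| Event rate p | n = 39 | n = 43 |
|---|---|---|
| 2% (assumed) | 45% | 42% |
| 5% (assumed) | 13.5% | 11.0% |
| 10% (Protocol placebo) | 1.6% | 1.1% |
| 15% (assumed) | 0.18% | 0.09% |
| 28% (Protocol active) | 0.0003% | below 0.0001% |

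The column for 43 is 39/0.9, the approximate number per arm once patients with missing endoscopy are imputed.

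**3. What happens to the estimate.** Take assumed counts of 11/39 (28%) on active and 0/39 on placebo.

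- Maximum-likelihood logistic: log odds ratio about 22.6, SE about 12,724, Wald p about 0.999. This is the non-estimable case that SAP 6.4 describes. With treatment removed there is no logistic comparison.
- Fisher, one-sided: C(39,11)/C(78,11) = 0.0002.
- Mantel-Haenszel: expected events 5.5; variance 39 × 39 × 11 × 67 / (78² × 77) = 2.393; z = 5.5/1.547 = 3.56; one-sided p = 0.0002; risk difference 28 points. Splitting the same counts over four assumed strata gives z = 3.49, p = 0.0002.
- Firth (for a 2×2 table, add 0.5 to each cell): OR = (11.5 × 39.5)/(28.5 × 0.5) = 31.9, log OR 3.46, SE 1.48. Wald z = 3.46/1.48 = 2.34, one-sided p about 0.01, 90% CI about 2.8 to 366.

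**4. An empty arm is not always strong evidence.** For 4/39 versus 0/39, one-sided Fisher p = C(39,4)/C(78,4) = 0.058 and Mantel-Haenszel p = 0.021.

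**5. Mixed separation across imputations.** Suppose none of 39 observed placebo patients remits and about 4 more are imputed (43 − 39). If each is imputed as a remitter with assumed probability 10%, 0.9⁴ = 66% of the datasets separate and 34% do not. At 5%, 0.95⁴ = 81% separate. SAP 6.4 does not say which model is then fitted.

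**The case against.** The strongest defence is that the comparison survives elsewhere. SAP 4.3.2 and 4.3.3 already plan a stratified CMH test and risk difference, which work with an empty arm (step 3). This stands: only the logistic result is at risk. It does not dispose of the point, because SAP 7.4.1 names logistic regression for the imputed data while referring back to Section 4.3, which names CMH for the same proportions. The SAP does not settle which result decides the first secondary test.

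Second, the rule says that the variable may be removed, so a sensible analyst would drop a sparse covariate and keep treatment. Removal is indeed discretionary, but nothing guides that discretion and its use need not be reported.

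Third, SAP 7.2 can be read as the default and SAP 6.4 as the contingency; the subgroup ANCOVA in SAP 6.2 also lists no separate stratification terms. That is a fair reading, but neither section refers to the other, so they still need reconciling.

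Fourth, an empty arm is unlikely. This stands. SAP 4.1 relaxes the rectal bleeding criterion for remission from 0 to 0 or 1, and that change can only raise the rate. Every remitter also meets endoscopic improvement, so that endpoint's rate cannot be below remission's.

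A reader might infer that the plan deletes the treatment comparison exactly when the effect is strongest. The documents do not support that: removal is optional, CMH remains, and 4/39 versus 0/39 is an empty arm with modest evidence. Nor do they support large probabilities of empty arms in subgroups, since the only subgroup model visible in SAP 6.2 is an ANCOVA on the 3-component score.

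**Conclusion.** The rule is defective as written, with limited reach. It permits removal of treatment or a stratification factor, does not require the removal to be reported, and is silent on imputed datasets that separate only in part. The consequence is loss of the logistic comparison, a conflict with SAP 7.2, or pooling of unlike models, depending on which term is dropped and where.

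The chance of no placebo remission is 1.6% at the protocol's 10% rate with 39 per arm, and 13.5% if the rate were 5%, which is an assumption. The primary ANCOVA is unaffected. Remission and response are exploratory with nominal p-values, so endoscopic improvement is the only binary endpoint in the formal sequence. The correction is worth making because it costs little and removes an unguided decision after unblinding; it does not threaten the study's main conclusion.

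**What to change.** Replace the separation sentence in SAP 6.4 and the reporting sentence after it with:

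> Treatment and the two stratification factors are never removed. If separation occurs in any imputed dataset, all datasets for that endpoint are fitted by Firth penalised-likelihood logistic regression with the same pre-specified terms, the already planned stratified CMH test and risk difference are reported beside it, and the change is noted in the results table.

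The cost is this SAP text and the Firth option in the logistic procedure. There are two downsides. Firth shrinks estimates slightly towards no effect. Rubin pooling of estimates and standard errors gives Wald-type inference, which is conservative here: about 0.01 one-sided for 11/39 versus 0/39, against 0.0002 by CMH or Fisher. That is why the CMH result should stand beside it. The new text does not decide whether CMH or logistic regression governs the first secondary test; SAP 4.3 and 7.4.1 should be aligned on that separately.

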6.5 Data/Study Reviewing Committees

The Data Safety Monitoring Board (DSMB) will monitor emerging study safety data and has the responsibility to review specific safety data reports, and to request additional reports as needed. Unblinded data reports generated by the unblinded statistician will be reviewed for adverse treatment effects and patient safety. The DSMB must keep results from blinded and unblinded data reports confidential. The roles and responsibilities of the DSMB will be outlined in a separate charter.

7 STATISTICAL TECHNICAL ISSUES

7.1 Planned Statistical Power and Sample Size

For the comparison of the primary efficacy measure in PMS#1 (including subscores for stool frequency, rectal bleeding and findings of flexible proctosigmoidoscopy) change from baseline, a sample of ~39 evaluable patients (having non-missing PMS at baseline and at Week 12) per group will provide approximately 80% power to detect a difference of 1.15 at $\alpha=5\%$ (1-sided test) based on an estimated pooled standard deviation 2.03. Sponsor will enroll sufficient patients to reach at least 117 evaluable patients.

7.2 Method of Assigning Participants to Treatment Groups Study

Patients who meet all the entry criteria and are eligible for the study will report to the investigator to be randomized on Day 1. Sites will randomize eligible patients for entry into the study in a 1:1:1 ratio to receive once daily doses of 1 mg APD334, 2 mg APD334, or matching placebo across the entire study, and is not constrained within a center. Randomization will be stratified by presence or absence of current oral corticosteroid usage and previous exposure to TNF α antagonists. All pre-specified efficacy analysis model will include for these two factors using CRF recorded data. Potential discrepancy between CRF recorded data and IVRS data entered by site staff will be investigated. A post-hoc analysis may be performed to evaluate the impact on main study endpoints caused by such discrepancy.

7.3 Blinding/Unblinding

The sponsor, patients, and personnel involved with the conduct of the study, with the exception of the clinical supply staff, safety staff, and the unblinded statistician supporting the Data Safety Monitoring Board (DSMB), will be blinded to the identity of study medication until the database lock. Blinding is accomplished by the random, masked, assignment of allocation numbers to the treatment groups, and by ensuring the drug supplies administered in the treatment groups appear identical. The contract research organization (CRO) will obtain written consent from Arena prior to breaking the code.

Breaking of the randomization code without Arena permission is expressly forbidden except in the event of a medical emergency where the identity of the study medication must be known in order to properly treat the patient. In the event of a medical emergency, it is requested that the investigator make every effort to contact the study monitor or designee prior to breaking the code. If the blind is broken, the individual responsible should document the date, time, and reason for breaking the blind. A written communication should be sent to Arena within 1 working day.

7.4 Handling of Missing Data and Sensitivity Analysis

7.4.1 Multiple Imputation for Primary Efficacy Analysis

Multiple imputation has 3 distinct phases: Imputation, Analysis and Combining. During the Imputation Phase, the missing data values are filled-in to form a complete dataset. This is done

‘m’ times. For the Analysis Phase, each of the ‘m’ complete datasets are analysed by a statistical model (as specified in Section 4.3 for each endpoint). The Combining Phase pools the parameter estimates with their standard errors across the ‘m’ complete datasets and produces an average estimate with a standard error calculated using Rubin’s formula^{9,10} this allows for the uncertainty between imputations as well as the variability within each analysis.

Multiple imputation assumes that the data are missing at random (MAR). MAR assumes that the missingness does not depend on the actual missing values, but that the missing data can be completely explained by the observed data. To test the robustness of the multiple imputation strategy a tipping point analysis may be implemented.

A tipping point analysis may be implemented for the primary endpoint to explore the influence of missing data on the overall conclusion of the primary efficacy analysis results. In this analysis, a wide spectrum of assumptions can be imposed regarding the missing data (from less conservative to more conservative) to find the “tipping” point assumption, at which conclusions change from being favorable toward APD334 to being unfavorable. After such a tipping point is determined, clinical judgment can be applied as to the plausibility of the assumptions underlying this tipping point. A delta (δ) method is often used to clearly formulate clinical assumption about Missing Not At Random (MNAR) mechanism. More specifically, the assumption is that, after dropout, subjects from APD334 have, on average, their PMS score worsen by some amount δ ($\delta = 0$ to 9, with a max PMS score of 9) from the time of dropout to Week 12.

Whether the missing data pattern is monotone or arbitrary (non-monotone), a fully conditional specification (FCS) method^{11,12} with predictive mean matching for continuous variables^{13,14} can be used. The FCS method allows for separate conditional distributions for each imputed variable. The predictive mean matching approach creates a regression model using parameters sampled from the posterior distribution and then a predicted value for each missing value is computed. The missing value is replaced by randomly selecting an observation from a set of ‘k’ values that are the closest predicted values to the missing predicted value.

In the case of Mayo scores, a multiple imputation approach is implemented for the missing individual components of the Total Mayo Score (TMS), which include stool frequency, rectal bleeding, findings of flexible proctosigmoidoscopy (endoscopy), and physician global assessment. Each individual subscore is imputed and then the composite endpoint measures are created (see list of endpoints below) following the specified algorithms or formulas in the SAP. The rectal bleeding, stool frequency, endoscopy, physician’s global assessment, treatment, stratification factors (oral corticosteroid use and prior exposure to TNF α antagonists), biomarker variables (e.g. [REDACTED]) inform the imputation model. The imputation model may include all these variables at all planned time points (e.g. Screening, Baseline, Week 1, 2, 4, 8, 12 and may be specific for each variable). These variables are included because they are correlated with the endpoint and/or missingness. The multiple imputation process creates [REDACTED] complete datasets using PROC MI in SAS 9.4. During post-processing, the endpoints are derived in each of the [REDACTED] complete datasets. The endpoints and analysis model in parentheses are listed below:

- PMS#1 (bleeding, stool, endoscopy) change at Week12 (ANCOVA)

[figure not shown]
- %-endoscopic improvement at W12 (Logistic regression)
- 2-component Mayo scores (bleeding, endoscopy) change at Week12 (ANCOVA)
- Total Mayo score (4-component) change at Week12 (ANCOVA)
- [REDACTED]
- %-clinical remission at Week12 (Logistic regression)
- %-clinical response at Week12 (Logistic regression)
- [REDACTED]
- Endoscopic score change at Week12 (ANCOVA)
- [REDACTED]
- Combination of clinical remission and response (trichotomy) at Week12 (Ordinal Logistic)

An analysis model (e.g. ANCOVA or Logistic as specified in the Section 4.3) for each endpoint is run on each of the [REDACTED] multiply imputed datasets. Thus, for any estimator of interest, there will be [REDACTED] estimates with standard errors obtained; these are pooled using PROC MIANALYZE to produce an overall estimate [REDACTED] and a standard error (based on Rubin's formula) with associated confidence interval and p-value. [REDACTED]

The multiple imputation model will be pre-defined before database lock. However, there could be certain adjustments due to unexpected data issues after unblinding treatment and [REDACTED]. All post-unblinding modifications to the multiple imputation model or approaches to address missing data will be described in the Clinical Study Report.

